#### **12.4.1.1 Primary and key-secondary efficacy variables**

Testing of the primary, co-primary and key-secondary efficacy variables will be performed in a 4-step approach using a hierarchical test procedure as described in detail below.

The primary efficacy variable is the change from baseline in AS in the primary clinical target pattern, i.e. elbow flexors or wrist flexors, at Day 29 (Week 4) of MP. A mixed model repeated measurement analysis (MMRM, two-sided, significance level  $\alpha=0.05$ ) with comparison of least square means will be used for the confirmatory analysis to detect differences between the high and low dose treatment groups. The dependent variable is the primary efficacy variable. The independent variables are defined as

treatment group (high dose, low dose), site (or pooled sites), BoNT-A pre-treatment status (pre-treated, treatment naïve) as fixed factors, visit\*treatment as interaction term, and visit as repeated factor. The covariates are the AS score of the primary clinical target pattern at baseline (Day 1 of MP) and the GMFCS level at screening.

Co-primary efficacy variable: An ANCOVA approach (2-sided, significance level  $\alpha=0.05$ ) with comparison of least square means will be used for the confirmatory analysis of the co-primary efficacy variable. The dependent variable is defined as the 'Investigator's GICS at Day 29 (Week 4) of MP'. The independent variables are defined as treatment group (high dose, low dose), site (or pooled sites), BoNT-A pre-treatment status (pre-treated, treatment naïve) as fixed factors and the covariates are the maximum AS score of the two possible primary clinical target clinical patterns flexed elbow or flexed wrist at baseline (Day 1 of MP) and the GMFCS level at Screening Visit.

Sites might be pooled for the statistical analysis, e.g., based on geographic criteria. If applicable, pooling of sites will be defined in the SAP.

Both, the primary efficacy variable and the co-primary efficacy variable have to show statistically significant treatment differences in order to prove superiority of high dose vs. low dose treatment.

Confirmatory testing will be performed on the FAS of MP with accounting for missing values by using MMRM approach for the primary efficacy variable. . In case of missing data in the co-primary efficacy variable these will be imputed by "0" (no change) (see [Section 12.4.7.1](#)).

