Baseline Injection Visit (V2): Day 1, randomization

Telephone Contact (TC1): Day 8 (Week 1) ± 3 days of MP

Ctrl. Visit (V3): Day 29 (Week 4) ± 3 days of MP

Ctrl. Visit (V4): Day 57 (Week 8) ± 3 days of MP

Optional Telephone Contact
Wk12: Day 85 (Week 12) \pm 3 days of MP

Final Visit of MP (V5) Day 99 (Week 14) \pm 14 days of MP

Open-Label Extension Period (OLEX)

Injection Visit (V6, V10, V14): Day 1 of the 2nd to 4th treatment cycle.

Telephone Contact (TC)
(TC2, TC3, TC4): Day 8 (Week 1) \pm 3 days of 2nd to 4th treatment cycle.

Ctrl. Visit (V7, V11, V15): Day 29 (Week 4) \pm 3 days of 2nd to 4th treatment cycle

Ctrl. Visit (V8, V12, V16): Day 57 (Week 8) \pm 3 days of 2nd to 4th treatment cycle

End of Cycle Visit (V9, V13) Day 99 (Week 14) \pm 14 days of 2nd and 3rd treatment cycle

End of Study Visit (V17): Day 99 (Week 14) \pm 14 days of 4th treatment cycle.

Revisit for reinjection

If any eligibility criterion is not met either at the Final Visit of MP (V5) or at an End of Cycle Visit in OLEX (V9 or V13), the injection may be rescheduled within up to 16 weeks after the last injection treatment.

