4 DETERMINATION OF SAMPLE SIZE

The sample size estimation for the primary efficacy variable 'change from baseline in AS in the primary clinical target pattern, i.e. elbow flexors or wrist flexors, at Day 29 (Week 4)' was based on data of a study with BoNT-A in the treatment of post-stroke UL spasticity in adults [Childers 2004 (1)]. In this trial a modification of the original 5-point AS to a 9-point scale by adding 4 half point increments was used. Since this modified Ashworth Scale (MAS) is very similar to the original Ashworth Scale (AS) used in the present study, it appeared to be justified to base the sample size calculation on the MAS results of the study by Childers et al.. In this study, a mean change from baseline in MAS scores at the elbow of -1.01 in the 180 U BoNT-A dose group and of -0.7 in the 90 U dose group were observed. It was assumed that the changes from baseline in AS for flexed elbow will be comparable to the one for flexed

wrist. The 180 U dose lies between the 200 U and the 150 U (for subjects ≥ 25 kg) doses planned for the high and mid dose group in this study. Since published trial data for the exact doses planned in this trial did not exist, and doses of BoNT-A applied in spasticity show complex non-linear correlations to AS scores [Yablon 2011 (2)], it appeared to be justified to use the same assumptions for both dose groups.

Comparable Placebo (PBO)-controlled studies showed a low drop-out rate of 3% at the time of assessment of the primary efficacy variable. Therefore, a similarly small number of missing data for the primary efficacy endpoint was expected for this study. Consideration of assumptions above with a 3% rate of missing values and using last observation carried forward (LOCF) as originally planned in the CSP led to the group means $\mu_{NT201_high} = -0.98$, $\mu_{NT201_mid} = -0.98$ and $\mu_{NT201_low} = -0.68$.

The assumption for a pooled common standard deviation (SD) was $\sigma = 0.6$.

An estimated total number of 258 (with randomization ratio of 2:1) subjects will provide 96.5% power to show a statistically significant difference between the NT 201 high dose group (172 subjects) and the NT 201 low dose group (86 subjects) at an alpha level of 0.05 (two-sided t-test, Statistical Analysis System software[®]).

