6.1.2 Co-primary, Key-Secondary and Secondary Efficacy Variables

The co-primary efficacy variable, the key-secondary efficacy variables and the secondary efficacy variables will be determined for MP only.

- Co-primary efficacy variable is the Investigator's Global Impression of Change Scales (GICS) for upper limb at Day 29 (Week 4) of MP. The definition of this variable was changed compared to the CSP (for details see section 8).

The GICS are subjective global outcomes to assess independently the investigator's, child's/adolescent's, and parent's or caregiver's (if applicable) impression of change due to treatment. Caregiver(s) may substitute parent(s) for the assessment of GICS, if they are main social contacts of subjects, e.g. in a special-care home.

The question of the GICS for the investigator is: 'Based on your clinical experience, what is your overall impression of change of the subject's upper limb spasticity due to treatment, compared to the condition before the last injection? Please check the one option that best fits your overall impression of change.'

The response option for all GICS versions is a common 7-point Likert scale that ranges from -3 = very much worse to +3 = very much improved:

- +3 Very much improved
- +2 Much improved
- +1 Minimally improved
- 0 No change
- 1 Minimally worse
- 2 Much worse
- 3 Very much worse

Key-secondary efficacy variables are:

- Change from baseline in AS score of the **other treated main clinical target pattern** (i.e. of elbow flexors or wrist flexors, if treated) at Day 29 (Week 4) of MP. This analysis will be performed for the main clinical target pattern not analyzed as primary efficacy variable, in case two target patterns would qualify as main clinical target pattern.
- Change from baseline in AS score of treated clinical target pattern clenched fist (in subjects treated in combination with flexed wrist) at Day 29 (Week 4) of MP.

Secondary efficacy variables are:

- Change from baseline in AS score for each treated clinical pattern (e.g., flexed elbow, flexed wrist, clenched fist, pronated forearm and thumb in palm) of the UL at all other post baseline visits of MP (V3, V4, and V5). The definition of this variable was made more precise compared to the CSP (for details see section 8).

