7.1.1 Primary Efficacy Variable

The primary efficacy variable is the change from baseline in AS in the primary clinical target pattern, i.e. elbow flexors or wrist flexors, at Day 29 (Week 4) of MP. A mixed model repeated measurement analysis (two-sided, significance level $\alpha=0.05$) with comparison of least square means will be used for the confirmatory analysis to detect differences between the high and low dose treatment groups. The following working hypotheses will be tested by use of a two sample t-test:

$$H_0: \mu_{NT201_high} - \mu_{NT201_low} = 0 \quad \text{vs.} \quad H_1: \mu_{NT201_high} - \mu_{NT201_low} \neq 0$$

with μ denoting the mean change from baseline. Stronger negative differences between least square mean estimates as defined by the working hypotheses thereby indicate better results (stronger reduction of AS from baseline to V3) in the high dose group compared to the low dose group.

Estimates for least square means will be derived from the mixed model repeated measures where the dependent variable in the model is defined as the change from baseline in the AS. The independent variables are defined as treatment group (high dose, low dose), pooled sites, BoNT-A pre-treatment status (pre-treated, treatment naïve) as fixed factors, visit*treatment as interaction term, and visit as repeated factor. Covariates are the AS score of the primary clinical target pattern at baseline (Day 1 of MP) and the GMFCS-E&R level at screening. The following SAS code will be used:

```
proc mixed data = dataset;  
  class treatment site btx subject visit;  
  model AS_change = treatment site btx AS_baseline GMFCS  
    visit visit*treatment / solution ddfm=kr;  
  repeated visit / subject= subject TYPE=un;  
  lsmeans visit*treatment / diff cl pdiff;  
run;
```

Sites will be pooled for the statistical analysis based on geographic criteria. For definition of pooling rules please refer to section 7.7.6.

Confirmatory testing will be performed on the FAS of MP with accounting for missing values using the mixed model repeated measures (MMRM) approach.

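### The confirmatory MMRM shares one baseline-Ashworth slope across Weeks 4, 8 and 14; a baseline-by-visit term would guard the Week 4 contrast against a small, conditional loss of precision

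*SAP*

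**What the plan says.** SAP 7.1.1 gives the fixed effects as "model AS_change = treatment site btx AS_baseline GMFCS", followed by "visit visit*treatment / solution ddfm=kr", with the covariance set by "repeated visit / subject= subject TYPE=un". The accompanying text agrees: "Covariates are the AS score of the primary clinical target pattern at baseline (Day 1 of MP) and the GMFCS-E&R level at screening". Protocol 12.4.1.1 describes the same model, with "visit\*treatment as interaction term, and visit as repeated factor" and no interaction between baseline and visit.

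AS is assessed after baseline at V3 (Week 4), V4 (Week 8) and V5 (Week 14, plus or minus 14 days), so three visits share one baseline coefficient. Only the Week 4 difference is confirmatory. SAP 7.1.2 carries the model into the AS tests of steps 2 to 4. The Investigator's GICS is measured once in the Main Period and analysed by ANCOVA, so this point does not touch it.

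SAP 7.1.1 also plans Week-4-only models (LOCF and observed case) as sensitivity analyses. Each of these estimates its own Week 4 baseline slope. Neither document gives a reason for the common slope in the confirmatory model.

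**The concern.** The covariance is left free and the treatment effect may change from visit to visit, but the baseline slope is held constant. This trial offers reasons to doubt constancy. Treated patterns must start at AS 2 or more and the scale stops at 0, so a child starting at 4 has more room to improve than one starting at 2. That limit should matter most while the drug acts. V5 is the visit at which need for reinjection is judged. Protocol 7.2.1 asks for AS of 2 or more again, or investigator judgment at AS 1, so many scores are expected to have moved back towards baseline by then.

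If the slopes do differ, the Week 4 contrast uses a coefficient that is partly set by Weeks 8 and 14. What is at stake is precision in the confirmatory AS tests. The confirmatory model could then be less precise than its own Week-4-only sensitivity model.

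**Working it through.** **Inputs from the documents (SAP 4 and 6.1.1).** Group sizes 172, 86 and 86; mean changes -0.98 (high and mid) and -0.68 (low), a difference of 0.30; SD 0.6; two-sided alpha 0.05; about 3% missing at Week 4; baseline AS of treated patterns 2 to 4.

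**Assumptions, because the documents do not give them.** Baseline variance, visit-specific slopes, between-visit correlations, and residual SDs by visit.

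**1. The plan's power.** High versus low: SE = 0.6 × √(1/172 + 1/86) = 0.0792, and 0.30/0.0792 = 3.79; the noncentral t gives 96.5%. Mid versus low: SE = 0.6 × √(2/86) = 0.0915, and 0.30/0.0915 = 3.28; this gives 90.3%. Both match the SAP. They come from an unadjusted two-sample t-test and so assume no gain from baseline adjustment.

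**2. Formula.** Let b be the vector of true slopes at Weeks 4, 8 and 14, and Σ the residual covariance. The common-slope model estimates b_c = (1′Σ⁻¹b)/(1′Σ⁻¹1). In large samples with complete data, the Week 4 variance relative to a baseline-by-visit model is

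V = 1 + (b₄ − b_c)² × Var(baseline) / σ₄².

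**3. Numbers.** Take b₄ = -0.5, Week 8 midway between Weeks 4 and 14, and Var(baseline) = 0.34. Holding the total Week 4 SD at 0.6 gives σ₄² = 0.36 − 0.25 × 0.34 = 0.275. With equal residual SDs and a gap of 0.5, b_c = -0.25 and V = 1 + 0.0625 × 0.34/0.275 = 1.077. In the same way:

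| Week 4 to 14 slope gap | V, equal SDs | V, baseline variance 0.2-0.4 | V, Week 14 residual SD 70% of Week 4 | V, residual SD rising over visits |
|---|---|---|---|---|
| 0 | 1.000 | 1.000 | 1.000 | 1.000 |
| 0.2 | 1.012 | 1.006-1.015 | 1.03 | 1.005-1.007 |
| 0.3 | 1.028 | 1.015-1.035 | 1.06-1.08 | 1.012-1.016 |
| 0.5 | 1.077 | 1.040-1.096 | 1.17-1.21 | 1.033-1.046 |

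A less regular correlation pattern moves the 0.5 entry from 1.077 to 1.083. A gap of 0.6 (slopes -0.6/-0.4/0, residual SD 0.6, baseline variance 0.4275, correlations 0.6 adjacent and 0.45 otherwise) gives b_c = -0.324 and V = 1 + 0.276² × 0.4275/0.36 = 1.09. A simulation of 3,000 trials with those slopes gave SEs of 0.0838 and 0.0808, and (0.0838/0.0808)² = 1.08.

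**4. Simulation check** (172 versus 86, 3% missing, unstructured covariance, 300 trials per scenario):

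| True slopes, Weeks 4/8/14 | Variance ratio, common to by-visit | Mean model SE, common / by-visit |
|---|---|---|
| -0.5/-0.5/-0.5 | 0.999 | 0.0696 / 0.0696 |
| -0.5/-0.4/-0.3 | 1.013 | 0.0701 / 0.0697 |
| -0.5/-0.35/-0.1 | 1.043 | 0.0712 / 0.0697 |
| -0.5/-0.25/0 | 1.081 | 0.0728 / 0.0701 |

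Bias of the Week 4 contrast was at most 0.006 in either model. The simulation error is about 0.07/√300 = 0.004.

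**5. Effect on power.** With total SD held at 0.6, the largest equal-SD case (gap 0.5, baseline variance 0.4) is 98.9% against 99.3% for high versus low, and 95.6% against 97.0% for mid versus low. All four exceed the planned figures. If 0.6 is instead read as the SD after adjustment, V = 1.04 gives 95.9% and 89.2%, V = 1.10 gives 94.9% and 87.5%, and V = 1.20 gives 93.1% and 84.5%.

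**The case against.** The case for leaving the model alone is strong on several points.

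- **Unequal slopes are not documented.** No section reports slopes by visit, and protocol 6.2 treats duration of effect as something the study will learn. With equal slopes nothing is lost. This stands.
- **The direction is open.** A reader might infer that Week 4 is under-adjusted. For a change score the slope is Cov(follow-up, baseline)/Var(baseline) − 1. If correlation with baseline weakens over time, the later slopes could be the steeper ones, and Week 4 would be over-adjusted. Wear-off makes a steeper Week 4 slope plausible, no more. This stands.
- **Validity is intact.** A reader might infer a biased contrast. Randomization and about 3% missing data leave it essentially unbiased, and the unstructured covariance puts the slope misfit into the Week 4 residual variance, so the SE reflects it. This stands.
- **Planned power is safe.** A reader might infer that the trial is underpowered. The planned power takes no credit for adjustment. Even at V = 1.21, the Week 4 residual variance in the example is 0.275 × 1.21 = 0.333, an SD of 0.577, still below 0.6. This stands.
- **The Week-4-only models would expose a poor fit.** This stands only in part: as sensitivity analyses they cannot replace the confirmatory test.

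A common-slope MMRM is a legitimate prespecified model, and protocol and SAP agree on it. The case for change is only that the more flexible version costs almost nothing.

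**Conclusion.** A minor, low-cost refinement. The model does impose one baseline slope on three visits when only Week 4 is confirmatory. The resulting variance inflation at Week 4 is nil with equal slopes, about 1-4% with moderate differences, and about 7-9% with a gap of 0.5-0.6 at the central inputs (4-10% at a gap of 0.5 over baseline variances of 0.2 to 0.4). It approaches 20% only if a large gap coincides with much smaller Week 14 residual variance.

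All these sizes rest on assumed slopes, baseline variance and covariance, so they bound a possible loss and do not demonstrate one. The documents support no finding of bias, inflated type I error or overstated power. The only consequence beyond precision is that a chance baseline imbalance in a given trial would be corrected less fully.

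**What to change.** Before Main Period unblinding, add `AS_baseline*visit` to the MODEL statement of the confirmatory MMRM in SAP 7.1.1, after `visit*treatment` and before the slash. State that the same term applies to the AS analyses in steps 2, 3 and 4. Add the interaction to the covariate description in SAP 7.1.1, and record the departure from protocol 12.4.1.1 in SAP section 8.

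The cost is two fixed-effect parameters, negligible with 258 subjects (high versus low) or 172 (mid versus low). No new data, visits or subjects are needed. With equal slopes the simulated variance ratio was 0.999, so the term is essentially free when it is not needed.

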7.1.2 Co-Primary, Key-Secondary and Secondary Efficacy Variables

Co-primary efficacy variable:

1. Step: Both, the primary efficacy variable and the co-primary efficacy variable have to show statistically significant treatment differences in order to prove superiority of high dose vs. low dose treatment. No α -adjustment for multiplicity is necessary.

The co-primary efficacy variable is the Investigator's Global Impression of Change Scales (GICS) for upper limb at Day 29 (Week 4) of MP. As for the primary efficacy variable, an analysis of covariance (ANCOVA) approach (2-sided, significance level $\alpha=0.05$) with comparison of least square means will be used for the confirmatory analysis of the co-primary efficacy variable. The dependent variable is defined as the 'Investigator's GICS at Day 29 (Week 4) for upper limb of MP'. The independent variables are defined as treatment group (high dose, low dose), pooled sites, BoNT-A pre-treatment status (pre-treated, treatment naïve) as fixed factors and the covariates are the maximum AS score of the two possible primary target clinical patterns flexed elbow or flexed wrist at baseline (Day 1 of MP) and the GMFCS-E&R level at Screening Visit. The following SAS code will be used:

```
proc mixed data = dataset;  
  class treatment site btx;  
  model I_GICS_wk4 = treatment site btx max_AS_baseline GMFCS / solution;  
  lsmeans treatment / pdiff CL alpha=0.05;  
run;
```

Positive values for differences between least square mean estimates as defined by the working hypotheses (see primary efficacy variable) thereby indicate better results (higher GICS values at Day 29, Week 4) in the high dose group as compared to the low dose group. Confirmatory testing will be performed on the FAS of MP with replacement of missing data, setting all missing values of the co-primary efficacy variable to "0" (no change).

Further sensitivity analyses will be performed on the PPS as well as on the FAS of the MP and the PPS without missing replacement (observed case analysis).

Further, a non-parametric Wilcoxon rank-sum test will be performed as sensitivity analysis to investigate the impact of potential deviations from the assumption of normal distribution (for FAS and PPS subset, imputing missing data by "0", i.e. no change). The same SAS code as for the primary efficacy variable will be used with primary efficacy variable replaced by co-primary efficacy variable.

Furthermore, frequency tables and descriptive summary will be performed for the co-primary efficacy variable.

Key-secondary efficacy variables and co-primary efficacy variable restricted to subpopulation:

2. Step: If the confirmatory tests of the primary efficacy variables and the co-primary efficacy variable both show significant results, then the hierarchical testing approach will be continued in a second step. In this second step the following two variables will be tested for high dose group versus low dose group:

- First key secondary efficacy variable: Change from baseline in AS score of the **other treated main clinical target pattern** (i.e. of elbow flexors or wrist flexors, if treated) at Day 29 (Week 4) of MP
- Co-primary efficacy variable: Investigator's Global Impression of Change Scales (GICS) for upper limb at Day 29 (Week 4) for the following subpopulation:

This analysis will be done for the subpopulation defined by this key-secondary endpoint, that means only subjects having two main clinical target patterns will be included into the analysis. All subjects with only one main target pattern will be excluded from the analysis. The analysis models will be identical to the analyses described above for the 1st step using the the key-secondary variable instead of the primary variable and the co-primary variable restricted to the subpopulation instead of the co-primary variable of the unrestricted population.

Both, the first key-secondary efficacy variable and the co-primary efficacy variable for the subpopulation have to show statistically significant treatment differences in order to prove superiority of high dose vs. low dose treatment in this subpopulation.

3. Step: Only if the confirmatory analysis of step 2 yields a statistically significant result, in a third step, a confirmatory analysis of the second key-secondary efficacy variable 'change from baseline in AS score of clinical target pattern clenched fist (in subjects treated in combination with flexed wrist), at Day 29 (Week 4) of MP will be done. This variable has been chosen, since it is anticipated that the vast majority of subjects will have a combined clinical presentation of clinical patterns clenched fist and flexed wrist. Subjects with either treatment alone (i.e. clenched fist or flexed wrist) with other clinical target patterns will be evaluated separately in a descriptive manner as other efficacy variables (see also section 6.1.3 and 7.1.3).

4. Step: Only if the confirmatory analysis of step 3 yields a statistically significant result, in a fourth step, using a hierarchical testing approach, the mid dose treatment will be compared to low dose treatment for the primary efficacy variables and the co-primary efficacy variable. The analysis models will be identical to the analyses described above for the 1st step replacing high dose group with mid dose group. Both, the primary efficacy variable and the co-primary efficacy variable have to show statistically significant treatment differences in order to prove superiority of mid dose vs. low dose treatment.

For the confirmatory analyses a two-sided significance level of $\alpha=0.05$ will be applied and analysis models as described for the (co)-primary efficacy variables will be applied. The

analysis of the primary efficacy variable and of both key-secondary efficacy variables will be performed on the FAS of the MP with an MMRM approach. For the co-primary efficacy variable and the co-primary variable restricted to the subpopulation, missing data will be imputed by "0", i.e. no change.

All other test procedures will be explorative. Sensitivity analyses will be performed on the PPS of MP using the MMRM approach, as well as on the FAS and the PPS of MP using a mixed model approach without repeated measures first with the LOCF principle and second without replacement of missing values (i.e., observed case analysis). As the GICS is measured at Control Visit V3 only it is not possible to apply a model based analysis like mixed model repeated measurement.

Secondary efficacy variables:

All secondary variables will be analyzed on the FAS of the MP and the PPS. All tests will be descriptive and interpreted in an explorative manner. Treatment comparisons will be tested for comparison of the high versus low dose treatment group and the mid versus low dose treatment group, respectively.

Ashworth scale of the UL

The difference between treatment groups in the change from baseline in AS score for each treated clinical pattern (e.g., flexed elbow, flexed wrist, flexed fingers) of the UL at all other post-baseline visits will be analyzed by a mixed model repeated measurement analysis as described for the primary efficacy variable. Furthermore, descriptive summary statistics, shift tables and frequency tables of changes will be given. Besides the model based missing value imputation approach, a mixed model without repeated measures will be applied with missing values imputed by LOCF and observed case analyses.

Questionnaire on Pain caused by Spasticity

All analyses regarding the QPS will be performed separately for upper limbs and for lower limbs. The QPS child/adolescent score, the child/adolescent general pain intensity item, the QPS parent/caregiver score, and the parent/caregiver general pain frequency item will be analyzed by using descriptive summary statistics at all visits and for changes from baseline to all post-baseline visits. The child/adolescent general pain intensity item and the parent/caregiver general pain frequency item will additionally be analyzed by using frequency tables. All other single items of the QPS will be listed.

The QPS child/adolescent score and the QPS parent/caregiver score will be analyzed by an ANCOVA. The dependent variable is defined as the change from baseline in the QPS score. The independent variables are defined as treatment group (high dose and in 2nd step mid dose vs. low dose), pooled sites, BoNT-A pre-treatment status (pre-treated, treatment naïve) as fixed factors and the covariates are the QPS score at baseline (Day 1 of MP) and the GMFCS-E&R level at Screening Visit. LOCF as well as observed case analyses will be performed.

In these frequency tables of the child/adolescent general pain intensity item and descriptive summary statistics of the QPS child/adolescent score and the child/adolescent general pain intensity item and the ANCOVA of the QPS child/adolescent score, subgroup analyses will be done for the self-administered version and for the interviewer-administered version in addition to the pooled analysis. LOCF for the QPS child/adolescent score and the child/adolescent general pain intensity item will only be applied for the pooled version if both versions (self-administered and interviewer-administered) are missing. For the self-administered and interviewer-administered version no LOCF will be performed.

Not all children and adolescents are able to make the QPS assessment self-administered or interviewer-administered version at all visits, which will presumably lead to a high number of missing values for the QPS child/adolescent score and the child/adolescent general pain intensity item. For this reason observed case analyses of QPS child/adolescent score and child/adolescent general pain intensity item is of main interest and the LOCF analysis is only a sensitivity analysis, which must be interpreted with caution.

Global Impression of Change Scales

Child's/Adolescent's (if applicable) and Parent's/Caregiver's GICS for upper limb at Day 29 (Week 4) will be analyzed descriptively by an ANCOVA model as described for the co-primary efficacy analysis. Furthermore, frequency tables, Wilcoxon rank-sum tests and descriptive summary will be performed. Missing values will be replaced by "0" (no change) as for the co-primary efficacy variable and an observed case analyses will be performed. Not all children and adolescents are able to make the GICS assessment, which will presumably lead to a high number of missing values for the Child's/Adolescent's GICS. For this reason observed case analyses of Child's/Adolescent's GICS is of main interest and the worst case analysis is only a sensitivity analysis, which must be interpreted with caution.

[REDACTED]

[REDACTED]

[REDACTED]

[REDACTED]

[REDACTED]

[REDACTED]

[REDACTED]

[REDACTED]

[REDACTED]

[REDACTED]

[REDACTED]

[REDACTED]

[REDACTED]

[REDACTED]

[REDACTED]

[REDACTED]

[REDACTED]

[REDACTED]

[REDACTED]

[REDACTED]

[REDACTED]

[REDACTED]

[REDACTED]

[REDACTED]

[REDACTED]

[REDACTED]

[REDACTED]

[REDACTED]

[REDACTED]

[REDACTED]

